7.2 Analysis

7.2.1 Quantitative

Descriptive analyses will profile the participants in each setting. The primary outcome will be HIV SSK return; secondary outcomes will include acceptability measures, linkage to care, attrition rates and intervention uptake. Analysis will determine feasibility and sensitivity of outcome measures (testing, behavioural and economic) (27) for a definitive trial in each setting for each city.

7.2.2 Qualitative

A framework approach to qualitative data analysis will be used with the assistance of NVivo 10 software (28, 29). Taking each of the substantive areas of the question guides and questionnaires with qualitative open fields as a starting point, members of the research team will work in pairs to list the emergent themes arising from each data source, undertaking constant comparison with the data until each list is exhausted – a method that utilises both inductive and deductive processes (30). The themes will then be collated to ensure consistency, ensuring the elimination of overlap prior to thematic coding and analysis of the data.

7.2.3 Economic Evaluation

A positive diagnosis of HIV has significant cost and quality of life implications, the measurement of which are beyond the remit of this project, but are a key consideration in assessing the cost-effectiveness of an intervention to distribute SSK among Black African people compared to current screening methods. We will assess the feasibility of collecting information to inform key parameters for a life decision analytical model of SSK as a screening method for Black African populations by setting. These variables will include (i) the cost of the test including postage and packaging and any costs to services of giving out the test including training (ii) return rates (iii) cost of processing returned tests (iv) proportion of reactive and subsequently positive tests of those returned (v) clinical stage at diagnosis (vi) cost of confirmatory and additional testing on all reactive results and insufficient samples respectively. From this information a cost per test returned and a cost per positive and negative diagnosis can be calculated.

Models of HIV screening and the lifetime costs and outcomes associated with different screening methods are currently in development. We will assess the possibility of using previously developed decision analytical models for cost-effectiveness analysis that can report a life time cost per quality adjusted life year (QALY) gained of SSK sampling in different settings compared to current practice in Black Africans in the UK. In addition to the information mentioned above, prevalence and incidence of disease in this group are also likely to be important parameters for the model, along with other characteristics that differ to the UK general population. If suitable decision analytical models do not already exist one would need to be developed as part of a full trial.

We will conduct a budget impact analysis to determine the cost to commissioners of screening for HIV in Black Africans across current settings based on the number of Black African people in their local community; test uptake rates; cost per test and cost per positive diagnosis as calculated above, by setting; and cost of HIV treatment dependent on stage of disease.

7.2.4 Process evaluation analysis

Process data will be analysed at the end of the first month of recruitment in order to ensure that any essential modifications that are needed can be implemented as soon as possible. Analysis will focus on ability to adhere to intervention fidelity and key lessons learned should a future Phase III evaluation be deemed feasible. The findings will be written up in light of ongoing policy and development in the wider field of HIV testing, self-sampling and self-testing. The quantitative and qualitative data from the process evaluation will be analysed as detailed above.

8. Ethical Considerations

The study will be carried out in accordance with the principles of the 2008 Declaration of Helsinki; the 2005 Research and Governance Framework for Health and Social Care as well as UCL relevant regulations and with Good Clinical Practice.

8.1 Informed Consent

Prior to patient participation in the study, informed consent will be obtained from each patient. This will be done prior to the participant undergoing procedures that are specifically for the purposes of the study and are out-with standard routine practice in the two settings. On the consent form (appendix 2), each signature must be dated by each signatory and the informed consent and any additional patient information form retained by the investigator as part of the study records. All CBOs will adhere to the university standards of Data Protection. All study related data collection forms will be returned to the study team by the time that Phase 2 recruitment ends.

For participants who indicate their consent electronically via the study tablets, this will be obtained by checking a box to indicate willingness to participate. This is standard practice in online surveys. Participants will be informed that their personal study-related data will be used by the research team in accordance with the data protection law. Although the research team would like sites to provide reasons why people decline to take part in the study, participants will retain their right to refuse participation without giving reasons. This will be respected by the study team. Participants will remain free to withdraw at any time from the trial without giving reasons and without prejudicing their further access to services provided by the study sites.

8.2 Approvals

This document, along with any subsequent modifications and with the sample informed consent documents will be reviewed by an NHS Research Ethics Committee. Should a substantial amendment to the protocol become necessary, the patient consent form and patient information form will also need to be revised to reflect the changes to the protocol. These will be submitted to the NHS REC for approval. These updated forms will be used by all patients subsequently entered into the study and those currently in the study, if affected by the amendment.

8.3 Duty of Care

University College London Hospitals NHS Foundation Trust will be the organisation providing care to all participants who return a self-sampling kit, this will include those recruited from general practice and community settings. Given the sensitivities around HIV we wanted to ensure clinical experience in self-sampling and the provision of HIV results. UCLH does not currently provide a self-sampling or HIV result notification service for patients however it has strong links with the Central & North West London NHS Foundation Trust (CNWL) who do. CNWL run the Mortimer Market Centre, a centre of excellence for the management of sexually transmitted infections and who also offer an HIV self-sampling service via Freedom Health. Thus duty of care will pass to CNWL for those with reactive and indeterminate results, and those who have not provided a mobile number so as to be able to receive negative results via SMS. Duty of care will pass to the health care institution attended for any confirmatory testing.

8.4 Patient and Public Involvement

Our study team has included community representatives from its inception, aiming to facilitate effective research design that will optimise community sensitisation and engagement. The representatives have actively contributed to discussions on the feasibility of proposed designs and highlighted methods to refine the proposal. Two of the programme's co-applicants are representatives from community based organisations (CBO): [name] coordinates UK Community Advisory Board (UKCAB), a network of community HIV treatment advocates across the UK that spans over 500 members from across 120 organisations; and [name] has extensive experience of managing and coordinating African amplification of HIV prevention interventions in England, including for HIV prevention England through the BHA. They have each reviewed the plan of investigation and sought approval of the programme outputs through consultation with their community colleagues. It is through their input that we have ensured that the methods and proposed outcomes best reflect the needs, interests and social contexts of Black African people in the UK.

8.5 Expenses and benefits

Participants will not be expected to travel to any of the participating sites solely for the purpose of the study. As such there will be no reimbursements of travel costs. All qualitative interviews in Phase II will be over the phone and £10 voucher reimbursements will be arranged.

8.6 Reporting

The project manager will submit reports to the NIHR on behalf of the CI on request. At the end of the study, an end of study report and end of study notification will be submitted to the NHS REC, NIHR and UCL (study sponsor).

9 Safety Reporting

9.1 Patient safety

As indicated in section 4.4 we do not anticipate that the participants of the study will be exposed to risk which is significantly greater than the normal risk associated with taking an HIV test in standard practice. All participants with reactive and indeterminate results will be contacted by a senior health advisor with experience in giving these results by phone. They will also have expertise in providing or linking into any necessary support. This Health Advisor will also make a follow up phone contact with all participants with a reactive result to ensure linkage to care has occurred. This will also provide an opportunity to identify any unexpected consequences of the testing process.

[figure not shown]
In the event that participants have further questions about the study, the patient information sheet (appendix 1) has the contact details of both the project manager and the principal investigator of the study. They will be able to deal with any queries or concerns about the study. We have provided links to further HIV information and support in the patient information sheet. It is also possible that some people may object to and become upset at being targeted for the intervention, as stated in section 4.4 all recruiters will be provided training to ensure they are able to explain why Black African communities are being targeted and to reassure prospective participants that the intervention is intended as a health opportunity for their community rather than a stigmatising activity. If any adverse events are reported during the qualitative interviews, participants will be referred to appropriate support services.

9.2 Research staff safety

The risk to staff will be minimal as they will not come into face to face contact with participants. Qualitative interviews will be conducted by telephone. The risk for sites is not anticipated to be higher than usual when they provide care or outreach services. As such their usual safety protocols will be used during the study.

10. Data Management

The diagram below indicates how the data will be managed in the study:

10.1 Source data

CRF entries will be considered source data in the settings detailed in this protocol where the CRF is the site of the original recording (e.g. there is no other written or electronic record of data). All documents will be stored safely in confidential conditions. On all study-specific documents, other than the signed consent, the participant will be referred to by the study number rather than by name.

10.2 Access to data

Direct access to the study data will be restricted to authorised members of the study team to enable them to carry out their duties. Access will also be granted to authorised representatives from the Sponsor, other host institution and the regulatory authorities to permit any study - related monitoring, audits and inspections.

10.3 Data recording and record keeping

One database will be used for quantitative data in this study. The study database will be hosted on the UCL IDHS. UCL have established secure data transfer technology via the UCL Information Data Safe Haven for the transfer of sensitive data collected as part of medical research. The technology meets all the requirements of the NHS Information Governance Toolkit. Data is transferred into the system via a secure gateway technology which uses SSL/TLS. The Data Safe

Haven can only transfer data via an integrated data transfer system. All data transfers are controlled by the Information Asset Owner (Principal Investigator) and are SSL/TLS AES256 encrypted in transit and logged. By default, the transfer is limited to one download and data is removed from the file transfer gateway once downloaded. The environment does not allow the use of email or any other means, such as removable USB storage, to transfer files. Data can be uploaded by clinics directly into the UCL data safe haven (encrypted). Research team members are the only people who can access this data (via a password fob). IDHS supports a MS SQL Server database including Excel and RedCap packages. All study data will be entered on to paper CRFs and/or directly onto the IDHS database or study database as described in the data collection section 6.6. Data will be stored on the UCL server and is backed up to remove threat of loss of data. The UCL policy indicates that research data from a study such as this one is stored for five years after the study ends.

UCL and each participating site recognise that there is an obligation to archive study-related documents at the end of the study (30/09/16). The Chief Investigator confirms that he/she will archive the study master file at UCL IDHS for the period stipulated in the protocol and in line with all relevant legal and statutory requirements. The Principal Investigator at each participating site agrees to archive his/her respective site's study documents for 5 years and in line with all relevant legal and statutory requirements.

10.4 Confidentiality

All information related to participants will be kept confidential and managed in accordance with the Data Protection Act 1998, The Caldicott Report & Caldicott Principles 1997, NHS Confidentiality Code of Practice 2003, The Freedom of Information Act 2000, The Research Governance Framework for Health and Social Care, and the conditions of Research Ethics Committee Approval. During results management, any patient identifiable data, both transferred and stored, will be encrypted in line with NHS Information Governance 'Guidelines on use of encryption to protect person identifiable and sensitive information' 2008.

The unique ID number will identify all laboratory specimens, case record forms, and other records and no names will be used, in order to maintain confidentiality. All records will be kept in locked locations. Clinical information will not be released without written permission, except as necessary for monitoring by the study monitors. SMS use will adhere to the NHS and UCL Information Governance Information Risk Management guidance. Participant personal information will be stored on the secure university IDHS database. The software is designed to

securely collect the data from the online survey and ethical hacking will be used to ensure the level of security is maintained against current threats.

Semi-structured interviews with participants will be audio recorded and labelled with a unique number. All names (and other potentially identifying information) will be removed from audio recordings as soon as possible. Digital recordings and pseudonymised transcripts will be maintained in a password protected database on password protected UCL or LSHTM desktop computers. On transfer, the audio data will be deleted from the digital voice recorder. Digital recordings will be transcribed by a professional transcription company that provides secure encrypted data transfer within the UK, and has been deemed to meet UCL's data protection requirements. The subcontracted agency will be confirmed at a later date and a contractual arrangement will be put in place between the sponsor and transcription service. Recordings will be securely stored on password protected computers within a locked office and deleted after transcription. Transcripts will be kept in password protected computer files, and all potentially identifiable information (e.g. names) omitted from the transcripts.

11. Laboratory

The Doctors Laboratory (TDL), based at [name], will be contracted by UCLH (University College London Hospitals NHS Foundation Trust) to supply the kits and the processing of the samples for this study. TDL and UCLH already work together on a pathology joint venture, which aims to bring together the best aspects of all partners to ensure quality care for patients and best value for the health economy.

12. Study Committees

A study steering committee was established in August 2014. Study progress and interim analysis of data will be provided to the study steering committee every six months.

13. Finance and Insurance

The study is funded by the NIHR HTA Grant number 12/138/02. We will receive service support costs from the NHS in phase 2 for the NHS sites. The study is sponsored by the University College of London. UCL will provide insurance and indemnity cover for all participants.

University College London holds insurance against claims from participants for harm caused by their participation in this clinical study. Participants may be able to claim compensation if they can prove that UCL has been negligent. However, if this clinical study is being carried out in a hospital, the hospital continues to have a duty of care to the participant of the clinical study. University College London does not accept liability for any breach in the hospital's duty of care, or any negligence on the part of hospital employees. This applies whether the hospital is an NHS Trust or otherwise.

14. Dissemination and outputs

14.1 Dissemination of findings

We plan a multi-stage, multimedia and audience specific approach to disseminating the research findings to ensure that all communication is accessible and relevant to the target audience at local, regional and national levels. The primary beneficiaries of this research will include: 1) those who will ultimately undertake the definitive trial that follows on from this preliminary feasibility investigation; 2) commissioners and services planning SSK for HIV testing rollouts; 3) Black African communities; and 4) healthcare professionals and policy makers.

Dissemination levels and outputs: In addition to the main project report and intervention manual, we will employ a range of dissemination activities to ensure the diverse stakeholder groups are informed of our findings.

National level: A minimum of two scholarly articles in peer-reviewed, open access journals, a four page briefing paper written in accessible language in print and pdf formats, and oral presentation of the findings at clinical and non-clinical HIV conferences at national level (such as the BHIVA and BASHH, the national HIV Prevention England conferences and the Scottish National Sexual Health and Blood Borne Viruses Framework events). Following publication, copies of the briefing (in print or pdf) will be available freely from co-investigator and other relevant websites (eg.<http://i-base.info/>).

Regional level: The project team hold influence with current and potential providers of community-based HIV testing and prevention interventions including Health Watch, CCGs, Health and Wellbeing Boards, Public Health England, sexual health & HIV networks, clinicians, and other members of the British HIV Association; primary health care providers; as well as additional stakeholders including the National AIDS Trust, MedFASH, NICE, HIV patient advocacy groups such as UKCAB and the population of Black African people in the UK who are

most likely to have undiagnosed HIV. In Scotland, dissemination will be facilitated by [name] who is a member of the Scottish Government's National Sexual Health and Blood Borne Viruses Ministerial Advisory Committee.

Local level: Stakeholders and providers will be notified of project progress through strategic mailing lists, and targeted social media. These channels will be utilised to announce both the undertaking of the research process, as well as the release of the final report, journal articles and briefing sheets. We foresee that as a result of this, a minimum of 1,000 direct stakeholders will be informed of this work. Furthermore, to increase application and critique of the research results, we will hold two dissemination seminars (one in London, one in Glasgow) targeting invitations at a range of the most influential stakeholders (with attendees totalling approx 80).

The project team aims to enable practitioners and policy makers to apply our findings and guidance in a robust and timely manner. Our dissemination strategy has been developed to support this process. The strategy will leverage existing resources within the participating organisations, such as their academic infrastructure, professional relationships and community networks fully. We will work closely with UCL's well-established Public Engagement Unit. This unit and the UK-CAB will be integral to dissemination of findings beyond academic and policy forums.

14.2 Outputs

If our findings demonstrate that a Phase III trial is feasible then our primary output will be an intervention manual to enable replication in a subsequent UK wide Phase III RCT. The manual will include parameter estimates for the required sample size and a cost effectiveness analysis. It will provide guidance as to appropriate trial design for a given setting. The manual will enable a subsequent trial team to undertake the necessary processes for successful trial implementation.

We will compile a study report that summarises the key findings, and clearly outlines the methods utilised to design and deliver the intervention in each setting, for each population, and the rationales for the selection of study sites and sub-populations. The report will describe the processes of HIV SSK distribution, staff training, sample collection, communication of results and confirmatory testing.

Given that this is a feasibility phase II study, the routes to direct impact will follow through a subsequent trial and its outcomes. Nonetheless, there is little current evidence regarding the uptake of new HIV testing technologies among Black African people in the UK. This project will

provide evidence for NHS commissioners and service providers regarding the acceptability and feasibility of outcome evaluation and a budget impact analysis of screening for HIV across different settings. By examining the feasibility and acceptability within GP surgeries and community based organisations, we also provide evidence for alternate models for reaching Africans.

Trials and interventions to broaden access to HIV SSK are starting to emerge, but the proposed research offers an opportunity to extend the knowledge base. Additionally, we acknowledge that a range of statutory and commercial programmes seeking to expand distribution of SSKs to both narrowly and broadly targeted populations are already in place, and will continue to emerge throughout the course of the proposed research. The technology is already licensed and available (www.drthom.com, www.ruclear.co.uk).

Appendix 3 HAUS Study Participant Screening and Enrolment Log

Name of Person Screening and Enroling participants										
Site name and Address										
ID Number	Sex		Initials	Age (years)	Country of Birth	Screening Date (dd/mm/yy)	Enrolled?		Reason if not enrolled (insert number from list below) If Did Not Attend insert #11	Comments
	M	F					 Yes	 No		
							 Yes	 No		
							 Yes	 No		
							 Yes	 No		
							 Yes	 No		
							 Yes	 No		
							 Yes	 No		
							 Yes	 No		
							 Yes	 No		
							 Yes	 No		
							 Yes	 No		
							 Yes	 No		
							 Yes	 No		
1. Recently tested for HIV 2. Do not believe at risk of HIV 3. Prefer to test elsewhere 4. Prefer not to use a self-sampling kit 5. Prefer not to know HIV status 6. Do not like being offered an HIV test just because black African 7. Already knows is HIV positive 8. Prefer not to say 9. Other 10. Does not meet eligibility criteria 11. Did not attend										

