5.5 Secondary Outcome Measure

1. Point of delivery outcomes:
 - Acceptability of targeted HIV SSK distribution, including rationales for accepting or refusing the offer of an SSK
 - Acceptability and feasibility of targeted SSK distribution among specified service providers, including utility of protocols for SSK targeting, offers and intervention uptake.
2. Data collection outcomes:
 - Demonstration that intervention models and service provider training and support incorporates sufficient capacity to successfully record the numbers of: people offered SSK, accepting SSK, and returning SSK
 - Feasibility of collecting correct contact details enabling follow-up, reminders and communication of results
3. Pathway to care outcome measures:
 - Proportion of those whose samples are reactive who: a) are informed of results in person and b) who attend for confirmatory testing at an NHS setting of their choice
4. Overarching outcome measures:
 - Cost per person kit distributed and cost per HIV diagnosis per setting
 - Attrition rates and loss to follow up
 - Confirmatory testing, proportion of those receiving an HIV positive diagnoses, and clinical stage at diagnosis
 - Feasibility and sensitivity of outcome measures (testing, behavioural and economic) for a definitive trial.

6. Study Design

This is a prospective, mixed-methods, non-randomised study. The study evaluates the effectiveness of self-sampling for HIV as well as the cost effectiveness of distributing the SSK through GP settings and Community based organisations. Feasibility and acceptability will also be assessed through a process evaluation. Please see the fieldwork schematic diagram in section 6.1 for further information.

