6.6 Screening Procedures

6.6.1 GP Practices

Practice nurses will go through their patient list each morning and identify patients scheduled to visit in each session who are potentially eligible to participate in the study. The eligibility criteria indicated in section 6.3.1 will inform the screening process. The details of potential participants will be entered onto the screening and enrolment log (appendix 3). Only patients on the screening log will be offered the opportunity to take part in the study. Data on patients who are known not to meet the eligibility criteria will not be collected. Reimbursement for the time taken to screen for potential participants will be met through CRN research support costs (NIHR CRN in London and the Scottish Primary Care Research Network in Glasgow).

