6.7.2 Targeting and Recruiting

The distributor will aim to introduce and recruit eligible candidates to the research study. They will explain the benefits of participating and having an HIV. All distributors will answer questions and aim to alleviate any concerns participants may have. The script below initiates the recruitment process:

“We are currently involved in an important study that I wonder if you’d be interested in taking part in? We want to see if people will use HIV self-sampling kits. HIV treatments are so good now; that you can live a normal healthy life with HIV, and being on treatment also stops most people from passing on the infection. So we are trying to find new ways to offer testing as it’s the people who don’t know their HIV status who become unwell.

This study is looking at whether people from the Black African community would want to use these kits. It’s a great opportunity as most people don’t have access to them yet.

Testing is very easy. It's all in this kit, which you take home to use when it is convenient to you. Once you've collected the sample you put it in the envelope provided and pop it in the post.

A few days later you are contacted by a NHS health clinic via your mobile phone with the results. Most people testing will be negative. A few people will have a test suggesting they have HIV (this is called a 'reactive' test) and we would have to check the result is correct.

It's all completely private and confidential - no one, other than the clinic contacting you, will know your result unless you want them to. What do you think? Is this something that you may be willing to try?"

If answer = NO then go to section A

If answer = YES then go to section B

Section A

"That's absolutely fine. We would really like to understand why people do not want to participate in the study. On this card are some of the common reasons why people say no – "

(Hand participant card)

"Would you possibly be able to let me know if any of the numbers match with your own reason? And if so which numbers? Of course it is also ok if you do not want to give me a reason."

(Participant gives reason or declines to do so)

(If reason given then insert into participant screening and enrolment log)

(Contact ends)

Section B

"First we need to determine if you're eligible for the study. Are you aged 18 or older and do you consider yourself Black African?"

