6.7.3 Consent Process

Participants who are eligible and agree to take part in the study will be given either the paper consent form to complete or they can be given study tablets to complete the consent form online.

Participants will consent to the following:

- a) Taking part in the study.
- b) Supplying a telephone number that can be used to contact them.
- c) Receiving reminder messages if their sample is not received at the laboratory (optional).
- d) Contact by NHS provider to provide them with their result.
- e) Notification of their GP of the result (optional) and only in the GP setting.
- f) Additional contact by phone or email for a telephone interview to explore the process and acceptability of self-sampling (optional).
- g) Audio recording of telephone interviews (optional)

The screening log (appendix 3) will also function as an enrolment log. In it, distributors will detail all eligible patients, whether or not they have approached them and if they have agreed to take part or not, and if not the reason for refusal if provided.

Please note it is not our intention to specifically notify the GP when a participant recruited in their practice consents to participate. We are specifically requesting consent to inform the GP of the

HIV test result (be it negative or reactive). If consent is obtained then the GP will be made aware of the result and that participation has occurred. If consent is not obtained or if the sample is not returned to the laboratory for processing then the GP will not be informed. The GP of all those recruited via community based organisations will also not be informed of either participation or test result.

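### The screening log cannot show who was offered a kit, so the denominator of uptake, a secondary outcome, can only be bounded and may differ between GP and community settings

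*Protocol*

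**What the plan says.** Section 6.7.3 gives the log two facts per person: "distributors will detail all eligible patients, whether or not they have approached them and if they have agreed to take part or not". Section 5.5, item 2, requires that sites can "successfully record the numbers of: people offered SSK, accepting SSK, and returning SSK". Section 7.2.1 adds that "secondary outcomes will include acceptability measures, linkage to care, attrition rates and intervention uptake".

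The form itself is in Appendix 3. After identifiers, sex, age, country of birth and screening date, it has a yes/no box for enrolment, a reason column headed "Reason if not enrolled (insert number from list below) If Did Not Attend insert #11", and a comments column. Codes 1 to 6 are reasons a person might give for declining. The list ends: "7. Already knows is HIV positive 8. Prefer not to say 9. Other 10. Does not meet eligibility criteria 11. Did not attend".

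Rows arise differently in the two settings. In general practice (section 6.6.1), "Practice nurses will go through their patient list each morning and identify patients scheduled to visit in each session who are potentially eligible". Those names go on the log before contact, and only people on it may be offered a kit. In community organisations (section 6.6.2), workers identify people during outreach and other services, when the person is present.

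Section 6.11.3A describes the same log differently again: as covering people approached, with their refusals and acceptances, and as recording date of birth where the form asks for age.

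**The concern.** The text promises approach status and the form has nowhere to put it. A GP patient who was listed, came, and was not asked gets Enrolled = No and then either a code that does not fit (most naturally 9) or a blank. A refuser who gives an unlisted reason, or none, can look the same.

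Two things are at stake. First, uptake needs a count of people offered, and recording that count is itself one of the study's outcomes. Second, a refusal and a nurse not managing to ask are different feasibility findings, and an ambiguous row does not say which it is. Section 7.1 also promises a minimum data set on eligible people who chose not to take part; a person never asked made no such choice.

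Because GP rows precede contact and community rows follow it, unasked attenders are likelier in GP logs, so the denominator may mean different things in the two settings. A later analysis plan cannot repair this: approach status not captured at contact is lost.

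**Working it through.** **The plan's own figures.** Section 7.1 gives precision for the return rate at an assumed 50% return. The half-width is 1.96 × √(0.5 × 0.5 / n): for n = 600 it is 4.00%, and for n = 380 it is 5.03%, matching the stated 4.0% and 5.0%. The base is kits distributed, so these figures do not depend on the number offered. The protocol states no uptake figure.

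**What each log entry reveals.**

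| Entry in Appendix 3 | Was an offer made? |
|---|---|
| Enrolled = Yes | Yes |
| Codes 1–6 and 8 | Yes, an answer to an offer |
| Code 11 | No, did not attend |
| Codes 7, 9, 10, or blank | Not shown |
| Attended but not approached | No code exists |

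The Appendix 11 weekly distributor log does not fill the gap, because it asks only how many people were recruited. No other form shown supplies the count.

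**Bounds on uptake (enrolled / offered).**

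- Lower bound: every ambiguous row is counted as offered.
- Upper bound: no ambiguous row is counted as offered.
- Code 11 is removed in both.

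**Illustration.** The protocol gives no number screened or offered, so all of these counts are assumed: 1,500 logged, 600 enrolled, 150 (10%) did not attend, and 75 (5%) genuine refusals coded 9. U is the number who attended but were not approached, coded 9 or left blank. The remaining people, R = 1,500 − 600 − 150 − 75 − U, refused under codes 1–6 or 8. Codes 7 and 10 are set to zero.

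- True uptake = 600 / (600 + R + 75)
- Lower bound = 600 / (1,500 − 150) = 44.4%, whatever U is
- Upper bound = 600 / (600 + R)

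| U | R | True | Lower | Upper |
|---|---|---|---|---|
| 0 (0%) | 675 | 600/1,350 = 44.4% | 44.4% | 600/1,275 = 47.1% |
| 150 (10%) | 525 | 600/1,200 = 50.0% | 44.4% | 600/1,125 = 53.3% |
| 300 (20%) | 375 | 600/1,050 = 57.1% | 44.4% | 600/975 = 61.5% |
| 450 (30%) | 225 | 600/900 = 66.7% | 44.4% | 600/825 = 72.7% |

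With all ambiguous rows counted as offered, the log shows 44.4% in every line while true uptake runs from 44.4% to 66.7%. Counting them as not offered overstates uptake instead, by 3.3 points at U = 10% (53.3 − 50.0). The direction of error therefore depends on the handling rule, and its size on U. An offered yes/no field recovers the true value in every line.

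**The case against.** A reader might infer that people offered a kit cannot be counted at all and that uptake will be wrong. The form does not support that. Enrolment and codes 1–6 and 8 identify most offers, code 11 removes non-attenders, and the comments column could hold a note that someone was not asked. The intervention manual (section 1.3) also intends that every eligible person using the service is told about the study. If that happens, counting the ambiguous rows as offered is correct and the error is nil. This stands, and it limits the point to a bounded ambiguity. But section 6.7.3 itself allows for people not being approached, and Phase 1 (section 4.2.1) noted busy surgery schedules. Full approach is what the study should test, not assume.

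A reader might also infer a fixed bias against general practice. Take 100 listed, 15 absent, 25 present but unasked, and 60 asked, of whom 36 accept: true uptake is 36/60 = 60%, against 36/100 = 36% or 36/85 = 42% from the log, a gap of 24 or 18 points. Every one of these counts is assumed. The 36% ignores code 11. The 42% arises only if all 25 unasked rows are counted as offered; if they are set aside and all refusers carry codes 1–6 or 8, the log gives 60%. The result is a range of 42% to 60%, not a fixed gap, and the protocol states no formal comparison of uptake between settings.

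A third inference is that the script distorts the denominator because its line "First we need to determine if you're eligible for the study" follows a yes. Both settings already screen against section 6.3.1 before the approach, and Phase 1 stressed opening these conversations sensitively. Moving the question is a debatable preference, not a correction.

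It is fair to add that weekly logs, site visits and distributor focus groups will shed light on non-approach, and that section 7.2.4 reviews process data after the first month. These sources can explain the problem but do not supply the count. The electronic log is not shown and may already have the field.

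**Conclusion.** The mismatch is certain: section 6.7.3 promises approach status, Appendix 3 has no field or code for it, and section 6.11.3A defines the log's population differently. The consequence is that the offered count, and so uptake, can only be bounded, and the denominator may not mean the same in GP and community logs.

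The size is unknown. On the assumed counts the bounds are 2.7 points wide if nobody is missed (47.1 − 44.4), 8.9 points at 10% unapproached (53.3 − 44.4) and 28.3 points at 30% (72.7 − 44.4). Neither the direction nor the size of any bias follows from the protocol. The primary return rate and its precision are unaffected. This is a defect in a data collection form that touches secondary outcomes; it is worth correcting before recruitment because the missing information cannot be recovered afterwards.

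**What to change.** - Add to Appendix 3 a yes/no column for whether the person was approached and offered a kit, and a reason code for attended but not approached. Make the same change to the electronic log if it lacks them.
- Reconcile sections 6.7.3 and 6.11.3A with the form: state whether the log covers all eligible people or only those approached, and whether it records age or date of birth.
- Compute uptake as accepted / offered in both settings. Report GP reach separately, as offered / eligible attenders.

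The script can stay as it is. The cost is one column, one code and a few seconds per entry.
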